## **COVID-19 Modified Study Procedures:**

During COVID-19 restrictions, we will enroll participants over the phone. To do this, we will mail patients a COVID-19 specific patient invitation letter and the COVID-19 specific informed consent form 7-14 days prior to their scheduled clinic appointment. If the patient has not called and opted out of the study, we will call the patient the day before their scheduled appointment to assess interest. If the patient is interested in participating in the study, we will review the COVID-19 specific informed consent form, which includes a HIPAA authorization, in which we replace the wet signature that was originally obtained with an acknowledgement of the study details, risks, benefits, and the acknowledgement to disclose protected health information through the process of agreeing to participate in the study.

Once the participant has agreed to participate, we will then randomize the participant into either the intervention or control group for Aim 2. After the participant has been randomized, and we know what combination of devices they will be receiving, we will then mail the participant their specific devices with the correct device handouts that we would normally give in-person.

Upon receiving the package, a phone call will be conducted with a study team member in order to complete the baseline questionnaire and train the participant on their respective devices. Each participant will be walked through how to place their Cardiac Insight patch. If the participant so wishes, we can also conduct this study visit over a teleconferencing system, like Zoom. Before completion of the study visit, the study team member will arrange the date and time for the participant's 14-day follow-up visit, which will happen virtually. Our normal study protocol remains the same for the participant during this Aim 2 period. After this baseline visit is complete, we will mail the participant their \$100 gift card.

On the day of the participant's scheduled 14-day follow-up visit, a study team member will call the participant and complete the 14-day follow-up questionnaire. Upon completion of the questionnaire, the participant will be randomized into an Aim 3 arm. If the participant is randomized into the control arm for Aim 3, we will ask the participant to mail back all of their Pulsewatch devices via a prepaid package. We will then mail the participant their \$100 gift card. Our normal study protocol will be followed for the rest of these participants study period, which includes conducting a questionnaire over the phone 30 days later and mailing their \$50 gift card.

For participants randomized into the Aim 3 intervention arm, we will ask them to mail back their Cardiac Insight patches via a prepaid package. If the participant was in Aim 2 control and is now in Aim 3 intervention, we will mail them the Pulsewatch System and the AliveCor Kardia Mobile device. We will also mail them their \$100 gift card. If the participant was in Aim 2 intervention and is now in Aim 3 intervention, we will mail them the AliveCor Kardia Mobile device and their \$100 gift card. Upon receiving their devices, a study team member will conduct a phone call, or a Zoom call, with the participant to train them on their new devices. Our normal study protocol will be followed for the rest of these participants study period, which includes conducting a questionnaire over the phone 30 days later, mailing devices back via a prepaid box, and mailing the participant their \$50 gift card.

For participants who have agreed to complete an exit interview, the interview will take place over the phone upon completion of the participant's 14-day follow-up study visit. The fact sheet for this exit interview will be explained to the participant prior to completing the exit interview. We will include this fact sheet in the package we send to participants before completing their baseline interview, so the participant can have it to reference. If the participant misplaces the fact sheet, we will mail it to them again.

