## Questionnaire-

### Part II (only):

At enrollment and at their 14-day follow-up study visits, all Part 2 participants will complete a questionnaire that includes standardized scales to assess quality of life (QoL), depression, anxiety, and self-activation. Questionnaires will take approximately 45 minutes to complete. If a participant does not return for a follow-up study visit or is unable to complete an in-person questionnaire assessment, then a phone call will be made to the participant to see if they are willing to complete the questionnaire via a phone assessment. These participants will still need to return their devices to receive compensation. We will permit phone calls and assist with return by mail on a case-by-case basis.

We will compare changes from baseline to the 14-day follow-up in these measures between the Aim 2 intervention (n=90) and Aim 2 control (n=30) groups.

At the end of each participant's 44-day enrollment, they will complete a questionnaire either over the phone or in person, whichever is easier for the participant, to assess QoL, anxiety, and self-activation. This questionnaire will take approximately 20 minutes to complete. Participants who were not randomly chosen to use the Pulsewatch system for 30 days (Aim 3 control group) will receive compensation upon completion of the 44-day follow-up questionnaire. Participants who were randomly chosen to use the Pulsewatch system for 30 days (Aim 3 intervention group) will receive compensation upon completion of the 44-day follow-up questionnaire and return of their devices.

We will compare changes from the 14-day follow-up to the 44-day follow-up in these measures between the Aim 3 intervention (n=60) and Aim 3 control (n=60) groups.

We will create a short-form questionnaire assessment in the event that a participant is unable to complete the full questionnaire. The only difference between the full assessment and short form is that the short form will contain only outcome measurements for the questionnaire. Here is an overview of the variables our questionnaires will be collecting. We have uploaded all of our questionnaires to eIRB.

Measurement	Questionnaire Tool	Outcome or Stratifier	Baseline Assessment (All Part II)	14-Days Follow-up Assessment (Control)	14-Days Follow-up Assessment (Intervention)	44-Days Follow-up Assessme nt (All Part II)
Physical asses		•	•			
Vision	Questionnaire (4 items)	Stratifier	✓			
Hearing	Questionnaire (3 items)	Stratifier	$\checkmark$			

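### For remotely enrolled participants the baseline questionnaire follows Aim 2 randomisation and delivery of the devices, so the non-primary Aim 2 patient-reported change comparison rests partly on an arm-aware baseline

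*Protocol*

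**What the plan says.** Protocol section 11, COVID-19 Modified Study Procedures, describes remote enrolment in sequence. After verbal agreement, "Once the participant has agreed to participate, we will then randomize the participant into either the intervention or control group for Aim 2". Once the arm is known, "we will then mail the participant their specific devices with the correct device handouts that we would normally give in-person". Then: "Upon receiving the package, a phone call will be conducted with a study team member in order to complete the baseline questionnaire", and the same call covers training on the assigned devices. A later sentence on the exit-interview fact sheet confirms the order: "We will include this fact sheet in the package we send to participants before completing their baseline interview".

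The Questionnaire part of section 11 uses that baseline: "We will compare changes from baseline to the 14-day follow-up in these measures between the Aim 2 intervention (n=90", against 30 controls. The table of instruments marks the GAD-7, SF-12, CHAI, the two self-efficacy scales and the ARMS as outcomes at both baseline and day 14.

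At day 14 the same remote pathway takes the other order, with the questionnaire first: "Upon completion of the questionnaire, the participant will be randomized into an Aim 3 arm".

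The SAP is dated 11/20/18 and has no COVID-19 provision. Neither document requires the baseline to be completed before randomisation, and neither plans a check by enrolment pathway.

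**The concern.** A baseline used in a change score should not be open to influence by the allocation. Here the package reveals the arm. Controls receive only patches, while the intervention arm also receives a watch, and a phone where needed. Participants know that both arms exist, because the consent form describes the randomisation. The caller who takes the questionnaire also trains the participant on the assigned devices, so the interviewer knows the arm too.

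All the affected scales are self-reported. If learning the arm moves the answers (reassurance, disappointment or worry about being monitored), the two arms no longer share a common starting point. A reaction that fades by day 14 enters the change difference with opposite sign. A reaction that lasts is subtracted out, so the change score misses part of the effect of assignment.

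**Working it through.** **1. Order of steps, remote pathway (Protocol section 11)**

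| Stage | First | Then |
|---|---|---|
| Enrolment, Aim 2 | randomisation, then mailing of the arm's devices | baseline questionnaire |
| Day 14, Aim 3 | day-14 questionnaire | randomisation |

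For in-person enrolment, section 24 puts the questionnaire after consent for inpatients but does not say when randomisation happens. The point is therefore limited to the remote pathway.

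**2. What is touched**

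- *Aim 2 accuracy (AUC):* not affected, because it uses no questionnaire score.
- *Aim 3 arm comparison:* not affected, because both earlier questionnaires precede Aim 3 randomisation for remote participants.
- *Aim 2 change to day 14, 90 vs 30:* affected. It is not primary. The only patient-reported row in SAP Table 2 belongs to Aim 3, and the Aim 2 power paragraph covers the AUC alone.

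**3. The plan's figures**

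Neither document gives a power figure for the Aim 2 patient-reported comparison. The nearest is the SAP's Aim 3 effect size of .74 for 30 vs 30. A two-sided 5% t-test at 80% power gives .736, so it reproduces.

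**4. Scale of a possible bias**

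From the documents: 90 and 30 participants. Assumed: a two-sample t-test on change scores (the protocol says only that changes will be compared), equal SDs at both visits, baseline-to-day-14 correlation ρ of .5 or .7, remote share f of 25-75%, and a baseline shift b of .1-.3 SD in one arm, gone by day 14.

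- Standard error for an outcome with SD 1: √(1/30 + 1/90) = .211. Detectable difference at 80% power: .595 SD.
- SD of change in baseline SDs: √(2(1−ρ)) = 1.00 at ρ = .5 and .775 at ρ = .7. Detectable change difference: .595 and .775 × .595 = .461.
- Bias of the change difference: −f × b.
- Bias with adjustment for baseline: −ρ × f × b.

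With f = .5 and b = .2 (rejection rates from the noncentral t, 118 df, no true effect; signs dropped):

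| | ρ = .5 | ρ = .7 |
|---|---|---|
| Change-score bias, baseline SD | .10 | .10 |
| In standard errors | .10/.211 = .47 | .10/(.775 × .211) = .61 |
| Rejection rate of a nominal 5% test | 7.6% | 9.3% |
| Baseline-adjusted bias, SD | .05 | .07 |
| Rejection rate, adjusted | 5.8% | 7.5% |

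Over the assumed ranges the change-score bias runs from .25 × .1 = .025 to .75 × .3 = .225 SD. At ρ = .5 the rejection rate runs from 5.2% to 18.7% (normal approximation). The upper end needs the largest share, the largest shift and no persistence together.

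**5. Transient against persistent reaction**

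A simulation with f = .5, b = .2 and 3:1 allocation agrees with the formulas. With a transient shift the change score is biased by about −.10 and the day-14 difference by about 0. With a persistent shift the change difference is about 0 and the day-14 difference about .10.

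**The case against.** The strongest reply is that the documents show an arm-aware baseline, not a bias. The remote share and the size, direction and persistence of any shift are all unknown, and at the low end of the assumed ranges the test is practically at its nominal level. Section 10 frames the endpoint as what using the app does to patients. For that target, a baseline taken after allocation but before use is arguably a fair starting point. The protocol names the questionnaire before the training within the call, so use need not have begun. The GAD-7 also looks back two weeks, a window that may largely predate the package. Finally, day-14 answers are open-label in every pathway, which reordering the baseline does not change.

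Most of this stands as a limit on weight. It does not remove the point. The transient case is a bias under either target, nothing elsewhere in the documents corrects the order, and the contamination can be avoided at little cost. It is also fair that the t-test is an assumption. The protocol's t-test and regression are described for the Aim 3 comparison, and the SAP has no Aim 2 patient-reported analysis at all.

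**Conclusion.** The concern holds for participants enrolled under the COVID-19 procedures. Their baseline outcome scores are collected after randomisation, with the arm known to participant and interviewer, and these scores enter the Aim 2 change comparison. Whether this biases the result, and in which direction, cannot be told from the documents. Under the central assumptions of section 4 of the working, the bias is .10 baseline SD against a detectable .46 to .595, which is modest. It does not reach the accuracy analysis or the Aim 3 randomised comparison. This is an inexpensive improvement to a non-primary analysis, not a threat to the trial's main result.

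**What to change.** In the COVID-19 procedures, complete the baseline questionnaire by phone after consent and before Aim 2 randomisation and mailing. Keep the call after delivery for device training and patch placement. If call length is an obstacle, the outcome scales are the part that must come first. The protocol already foresees a short form limited to them, though for participants who cannot complete the full version.

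For participants already enrolled remotely, record the enrolment pathway and the date and time of both randomisation and questionnaire. In the SAP, name the analysis of the Aim 2 patient-reported comparison, and add a sensitivity comparison of day-14 scores between the randomised arms that leaves out the post-randomisation baseline. State with it that:

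1. day-14 reporting is still open-label, so only the baseline contamination is removed;
2. it estimates the effect of assignment, including any lasting reaction to allocation;
3. its detectable difference is .595 day-14 SD if all 90 and 30 are scored.

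**Cost.** The consent call becomes longer or one call is added. On length the protocol says: "Questionnaires will take approximately 45 minutes to complete". The consent call falls on the day before the clinic appointment. For remote participants the baseline-to-day-14 interval grows by the delivery time. The variance of the sensitivity comparison relative to the change score is 1/(2(1−ρ)): equal at ρ = .5 and 1.67 times as large at ρ = .7.

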Research staff (RA or study coordinator) will provide enrolled participants with detailed instructions about the operations and proper usage of the Pulsewatch smartwatch, smartphone

apps (including the Pulsewatch app and AliveCor app), ECG, and 14-day monitor. A checklist and a YouTube video may be made available to participants to remind them of how to charge. wear, and perform ECG self-checks using the smartwatch and phone app. Participants (including all control and intervention participants) will return smartphones and watches and/or 14-day monitors after their study visit at 14 days. For Aim 2 intervention participants, pulse and ECG data from the smartwatch and annotations/adherence data from smartphones will be uploaded by study staff after the 14-day visit to the secure cloud server. Aim 2 control participants will be provided instructions on the gold-standard Cardiac Insight patches. Study staff will be available via telephone to answer any questions participants have with using the smartwatch and smartphone, charging the battery, and uploading data throughout the 14-day trial period as needed. The 60 randomly selected participants, who were consented at baseline to participate in this aim will receive additional training at their 14-day study visit, taught on how to use the AliveCor Kardia mobile device and will use the Pulsewatch smartwatch and smartphone for an additional 30 days. Participants in Aim 3's intervention group will be asked to upload pulse and ECG data from AliveCor if they would like to do a self-check after receiving the watch notification. The secure server architecture used by Samsung minimizes the potential for loss of health information and is similar to one used in our prior work.

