## Adherence Analysis:

In Aim 3 of Part II of the study, adherence will be operationalized to determine whether pulse recordings were present on each day over the 30-day period. We will examine whether participant characteristics, e.g., sex, cognitive impairment, or stroke-related quality of life, affect the likelihood of adherence over the 1-month study period. We will use a mixed effects logistic regression model, including the participant as the random effect to capture the correlation among repeated measures from the same participant, using participant characteristics as the fixed effects, and a binary indicator of daily adherence as the dependent variable. We will also examine the adherence time-trend by including time (day) as a fixed effect in the model and participant as a random effect to estimate the slope of adherence over time. To examine whether the time trend varies by participant characteristics, we will include the interaction between characteristics and time in the model so that the slope of adherence over time can be estimated for each category of participant characteristic variables and be compared among the categories (e.g., pAF diagnosed vs. no pAF). Secondary analyses will examine rates of adherence to Pulsewatch ECG prompts and will compare Pulsewatch users to the usual care group with respect to stroke-related quality of life, anxiety, and self-activation. We will calculate the change score between baseline and 1 month as a dependent variable. First, a t-test will be used to compare 2 study groups on the change score. We will use a linear regression model, which will include group indicator (Pulsewatch users vs. usual care) as the independent variable and possible confounders (e.g., medication adherence and participant demographics) as covariates, to estimate adjusted group differences on the change scores.

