**Part II:** We will use a rolling enrollment and randomization design with a goal of 90 participants completing the Aim 2 intervention and 30 participants completing the Aim 2 control group procedures (up to n=120 in the trial). To enroll patients who are admitted to UMMMC, RAs with access to the UMMMC neurology inpatient roster and cardiology/neurology ambulatory clinic schedules will screen the rosters daily to identify potentially eligible patients. We will screen any patient admitted with stroke or TIA to the neurology service (identified from the inpatient neurology roster admitting diagnosis) or presenting with a complaint potentially related to stroke (e.g., facial droop) and evaluated by the stroke service. For potentially eligible participants in whom the diagnosis of stroke/TIA is suspected (e.g., focal weakness), but not yet listed as a diagnosis, a neurology consultation note or history and physical examination documenting stroke/TIA will be needed to confirm eligibility. We will also screen cardiology patient rosters for any ambulatory patients who could have a CHA2DS2-VASc score  $\geq$  3 by looking at their medical problem list or provider notes.

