### **COVID-19 Modified Local Recruitment Methods**

During COVID-19 restrictions, we will screen both the cardiology and neurology ambulatory care clinics to identify eligible patients. When eligible patients are identified, they will be sent our

COVID-19 modified patient invitation letter 7-14 days prior to their scheduled appointment. As with our normal, IRB-approved patient invitation letter, there will be a number listed for the patient to opt-out of being contacted for the study. A day prior to their scheduled appointment, a study team member will contact the potential participant to assess interest in the study. If the potential participant agrees to participate, we will follow the consent and enrollment procedures outlined in Section 11: Procedures Involved.

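### Adherence and usability models have no term for in-person versus COVID-19 remote procedure, so characteristics unbalanced between the two could show biased associations

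*Protocol*

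**What the plan says.** **Standard procedure.** Section 24 of the protocol draws Part II participants from inpatient and ambulatory sources: "RAs with access to the UMMMC neurology inpatient roster and cardiology/neurology ambulatory clinic schedules will screen the rosters daily". Section 11 (Deployment of devices/app) has staff instruct participants on the devices, and those selected for Aim 3 use "will receive additional training at their 14-day study visit".

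**COVID-19 procedure.** Section 11 (COVID-19 Modified Study Procedures) states: "During COVID-19 restrictions, we will enroll participants over the phone". Baseline devices are mailed and training is by phone or video. At day 14, for an Aim 2 control who becomes an Aim 3 user, "we will mail them the Pulsewatch System and the AliveCor Kardia Mobile device"; an Aim 2 intervention participant who continues is mailed only the AliveCor device. Then "a study team member will conduct a phone call, or a Zoom call, with the participant to train them on their new devices". For recruitment, Section 24 says that "During COVID-19 restrictions, we will screen both the cardiology and neurology ambulatory care clinics to identify eligible patients" and names no inpatient source.

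**Analysis.** The Section 13 adherence model has a participant random effect, "using participant characteristics as the fixed effects, and a binary indicator of daily adherence as the dependent variable". Day and characteristic-by-day terms are added for time trends. The SAP's Aim 3 Analysis has the same structure. The Section 13 usability regressions also use participant-level factors. None of these names procedure or calendar period, and day means day within the 30 days of use. The COVID-19 sections say nothing about analysis.

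**The concern.** Who is recruited, how devices arrive and how people are taught are set by the study, and all three change together at a calendar point. Any of them could plausibly affect whether a daily pulse recording is present, which is the adherence outcome. Losing the inpatient stream could also plausibly change the mix on characteristics the plan wants to test, such as cognitive impairment or stroke-related disability.

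The comparisons between categories of a characteristic are not randomised, so nothing in the design balances procedure across them. If both links exist, part of the procedure or period effect is credited to the characteristic. At stake are the factors that the Aim 3 primary analysis reports as associated with adherence, and its false-positive rate. The usability regressions share the structure, but no size was worked out for them.

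**Working it through.** **1. The plan's own figure.** The SAP (Aim 3 Power) states detectable differences of 12–16 points at 50% adherence and 9–12 points at 80%, with 12 versus 18 users, 30 daily measures, auto-correlation .2–.5, 5% type I error (taken as two-sided) and 80% power.

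d = (1.960 + 0.842) × √{V × [p1(1−p1)/12 + p2(1−p2)/18]}

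- AR(1) correlation: V = [30 + 2Σ(30−k)ρ^k]/30², which is .049 at ρ = .2 and .096 at ρ = .5. Then d = 11.5 to 15.8 points at 50%, and 8.6 to 11.5 points at 80%. Both stated ranges reproduce.
- Constant correlation: V = (1 + 29ρ)/30, which is .227 and .517. Then d = 23.7 to 33.9 points at 50%. The stated range does not reproduce.

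The planned model has a participant random intercept, so correlation does not decay with time. With a random-intercept SD of 1 on the logit scale, the detectable difference at 80% adherence (other group lower) is about 19 points with 12 versus 18 users and about 13 with 24 versus 36. The SAP's 9–12 points is therefore not used as a yardstick below.

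**2. Bias from the omitted term.** Let r be the remote share, pI and pR the prevalence of the characteristic among in-person and remote users, and e the fall in adherence under the remote procedure. The characteristic has no true effect.

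P(remote | present) = r·pR / [r·pR + (1−r)·pI]

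P(remote | absent) = r(1−pR) / [r(1−pR) + (1−r)(1−pI)]

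bias = [P(remote | absent) − P(remote | present)] × e

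All inputs are assumptions; the documents give none of them.

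| r | pI, pR | e (points) | remote share: absent, present | bias (points) |
|---|---|---|---|---|
| .50 | .60, .20 | 20 | .40/.60 = .667, .10/.40 = .250 | .417 × 20 = 8.3 |
| .25 | .55, .25 | 15 | .1875/.525 = .357, .0625/.475 = .132 | .226 × 15 = 3.4 |
| .50 | .50, .40 | 5 | .30/.55 = .545, .20/.45 = .444 | .101 × 5 = 0.5 |

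If either the imbalance or e is zero, the bias is zero.

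**3. False-positive rate.** Simulation used at least 2,500 runs per setting, 30 daily binary values, random-intercept SD 1 and 80% in-person adherence. Each participant's mean adherence was regressed on the characteristic, with and without a procedure indicator. This stands in for the planned mixed logistic model.

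- Large inputs (30–40 point imbalance, 15–20 point effect, 25–50% remote): spurious difference about 3.5 to 8.5 points. Rejection is 11–32% with 60 users and about 7–18% with 30. With the procedure term, bias is about 0 and rejection about 5%.
- Small inputs (10–20 point imbalance, 5–10 point effect): spurious difference 0.3 to 2.2 points. Rejection is 4–7% with 60 users and 4–6% with 30.

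Both sample sizes are shown because the SAP plans 30 Aim 3 users and the protocol up to 60.

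**The case against.** **The bias is only conditional.** It needs both an effect of procedure or period and an imbalance, and the documents establish neither. This stands. A reader might infer that characteristics will absorb the procedure effect; the documents support only that they could. With modest inputs the error rate stays near 5%.

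**The quoted training call matters little for most users.** Continuing Aim 2 intervention participants receive only the AliveCor device at day 14, while the outcome is watch recordings. With 90 intervention and 30 control participants, about 60 × 90/120 = 45 of 60 Aim 3 users would already have had the watch for 14 days. This also stands, and it moves the relevant exposure to the first watch training, which is also remote for those enrolled under restrictions.

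**Procedure cannot be separated from period.** Pandemic behaviour and changed case mix coincide with mailed devices and phone training. This limits what the term means, but not the value of having it in the model.

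**The covariate lists are open-ended.** They are introduced as examples, so a term could be added later. But procedure is not a participant characteristic, and leaving the choice until after the data are seen invites selective modelling.

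**Stronger readings that do not hold.** One is to set the bias against the SAP's 9–12 points and call it close to a detectable effect. That figure reproduces only under AR(1) correlation, not under a random intercept. Another is to fault a SAP dated 11/20/18 for silence on COVID-19. That is chronology; the gap is that protocol Section 13 was not extended when the remote procedures were added. A third is to extend the point to the randomised comparison of Aim 3 users with controls. That comparison is less exposed, because allocation is random under both procedures.

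**Conclusion.** The gap is real: recruitment source, device delivery and training change partway through the study, and no adherence or usability model accounts for it. The consequence is conditional and its size unknown. On assumed inputs, the spurious adherence difference for a characteristic with no effect runs from under 1 point with near-nominal error to about 8.5 points with about 32% false positives at 60 users. These results rest on an assumed remote share, imbalance and procedure effect, a random-intercept SD of 1, and a linear analysis of participant means. That recruitment under restrictions is ambulatory only is also an inference: Section 24 names those clinics without excluding others. The point should be fixed because the remedy is nearly free, not because bias has been shown.

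**What to change.** - Record for each participant the procedure (in-person or COVID-19 remote) under which they were first trained on the Pulsewatch watch and app. That is Aim 2 baseline for Aim 2 intervention participants and the start of Aim 3 for Aim 2 controls. Coding everyone at the start of Aim 3 would misclassify those trained in person on the watch and remotely only on the AliveCor device.
- Add it as a fixed effect in the adherence models of protocol Section 13 and the SAP's Aim 3 Analysis.
- Where characteristic-by-day interactions are tested, add procedure-by-day as well; a main effect alone does not protect the slopes.
- Add the Aim 2 procedure to the Section 13 usability regressions.
- Report adherence by procedure beside the pooled rate, and state that the term reflects procedure and period combined, not the effect of remote training alone.

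Cost: one binary variable fixed at first training, one degree of freedom (two in the slope models) and a wording change. In the reruns without the slope interaction, the standard error of the characteristic effect changed by about 2%.
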